General Procedures. Figure 4 illustrates the study procedures and design. Interested individuals will be screened either by telephone or in person. Individuals who meet inclusion/exclusion criteria will be invited to come into the office for a comprehensive baseline assessment. Potential subjects will be given a full description of the study and asked to read and sign VA and MUSC IRB-approved informed consent forms before any study procedures or assessments are conducted. Ineligible individuals will be referred clinically for treatment. Consent will take place in a private office and will be conducted by trained staff, including the PI, Co-Is, Study Coordinator,

or Research Assistant. Baseline screening will involve further verification of diagnostic conditions (PTSD, SUD), a medical history and physical exam, assessment of concomitant medications, and breathalyzer and urine drug tests. Self-report measures of PTSD, substance use severity and other associated mental and behavioral problems (e.g., depression, anxiety, sleep functioning) will also be assessed at baseline and throughout the trial.

Complete medical evaluations will be conducted at baseline. This evaluation will include: physical examination including neurological examination; vital signs including orthostatic blood pressure and pulse measurements; weight and BMI calculation; and urine β -HCG in women with child-bearing potential. Laboratory testing including complete metabolic panel to include liver function test as well as an electrocardiogram will be conducted at baseline to ensure study eligibility. At other study visits conducted in person or via telehealth/phone, abbreviated assessments and adverse events will be reported and vital signs may also be recorded (e.g., blood pressure). Following the baseline visit, eligible participants may complete a neuroimaging session (described in the Neuroimaging Component section) and will then enter a 12-week, double-blind, placebo controlled medication trial during which they may be seen up to twice weekly for dosing and completion of assessments. Participants may complete another neuroimaging session during the last week of treatment. Then, participants may be seen again for a 6-week, post-treatment follow-up visit.

[figure not shown]

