Figure 4. Study design overview. Participants randomized to 12 wks of doxazosin (16 mg) or placebo. Up to twice weekly visits during wks 1-12, and a 6-week follow up. Neuroimaging scan prior to treatment initiation and again during week 12 prior to medication discontinuation.

Telephone Assessment: Participants in this research study may choose to do some of the weekly study visits via telephone, which may enhance retention by directly circumventing financial, transportation or other barriers associated with traveling to MUSC/VA clinics for in-person appointments. Telephone assessments will be delivered via MUSC/VA approved telephones.

Study Medication, Dosage, and Administration. Study medications will be prepared in the Compounding Lab at Plantation Pharmacy [name]. Plantation Pharmacy is a licensed Community and Compounding Pharmacy that is inspected regularly by the South Carolina Board of Pharmacy as both a retail pharmacy and a compounding pharmacy. Plantation Pharmacy is also a member of a national compounding supply, support, and education, company called Professional Compounding Centers of America (PCCA). Pharmacy staff involved in preparation of study medication are trained in the science and art of compounding and maintain all licensure and continuing educations requirements as dictated by the South Carolina Pharmacy Practice Act. Study medication and matching placebo will be encapsulated in standard-sized gelatin capsules, and be of sufficient opacity and color so as not to reveal contents inside or disclose any possible difference between placebo and active capsules. Commercially available doxazosin 8 mg tablets supplied by the primary investigators (DAVA 8mg tablets NDC 67253-0383-10) will be utilized as the source for active drug material for all strengths involved in the study. The tablets will be triturated to a fine, uniform powder to provide for the active ingredient source material. Capsule packing statistics been determined for each powdered component in the capsules. Each study capsule will contain 25 mg of riboflavin USP. The remaining volume in each capsule not utilized by active material and riboflavin will be back-filled to proper packing level with an inert filler of dextrose. Placebo capsules will consist of 25 mg riboflavin and be back-filled with dextrose in color-matched, opaque, identically sized capsules. Participants will be randomly assigned to receive doxazosin (target

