- Adverse Events (AEs): AEs will be assessed at baseline, weekly during treatment, and at follow-up. The type of AE, severity of the AE, duration of the AE, and relationship of AE to study medication will be recorded. The Study Physician ([name]) will evaluate and manage, as appropriate, reported AEs. All AEs, serious AEs (SAEs) and Unanticipated Problems Involving Risk to Subjects or Others (UPIRSOs) will be reported to the Consortium, DSMB, and the local IRB according to policies and procedures required by these entities.

- Concomitant Medications:** All concomitant medications will be recorded on a standard form throughout the study. Multivitamins supplied by the study will be recorded and inquiries will be made about daily compliance.
- Medication Accountability Log:** This is a document describing a one-week schedule recording days of study medicine taken. Returned medication packages will have capsules counted and recorded.
- Patient Blind Questionnaire:** This is a document asking the participant which medication he or she believed they received during the medication phase of the study.

Table 1. Assessment Instruments and Timeline

	BSL	Medication Initiation	Medication and Symptom Monitoring												F/U	
	Week →	-1	0	1	2	3	4	5	6	7	8	9	10	11	12	18
Informed Consent		X														
Demographics & Military Service Characteristics Form		X														
History and Physical Examination		X														
Health Questionnaire		X													X	X
MINI International Neuropsychiatric Interview (MINI) 7.0		X														
Adverse Events/Vital Signs		X	X	X	X	X	X	X	X	X	X	X	X	X	X	X
Concomitant Medications Form		X	X	X	X	X	X	X	X	X	X	X	X	X	X	X
Medication Adherence Log				2x	2x	2x	2x	x	x	x	x	x	x	x		2x
Riboflavin in Urine			X				X				X					X
Breathalyzer		X	X	2x	2x	2x	2x	x	x	x	x	x	x	x	x	2x
Urine Drug Screen		X			X			X			X					X
Pregnancy Test for Female Subjects		X					X				X					
Clinical Institute Withdrawal Assessment of Alcohol-Revised		X														
Clinician Administered PTSD Scale (CAPS-5)		X							X						X	X
Life Events Checklist for DSM-5 (LEC-5)		X							X						X	X
Deployment Risk & Resiliency Inventory-2 (DRRI-2) Combat Experiences and Postbattle Experiences		X														
PTSD Checklist (PCL-5)		X	X	X	X	X	X	X	X	X	X	X	X	X	X	X
Posttraumatic Cognitions Inventory			X		X		X		X		X		X		X	X
Childhood Trauma Questionnaire (CTQ)		X														
History of Head Injuries		X							X						X	X
Time Line Follow-[name] (TLFB)		X	X	2x	2x	2x	2x	x	x	x	x	x	x	x	x	2x

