Neuroimaging Component. Given the severe negative outcomes associated with co-occurring PTSD and AUD, investigating potential neural circuitry underlying PTSD/SUD as well as neural circuitry involved in positive therapeutic response to doxazosin could be important in guiding future studies targeting this circuitry using other therapeutic agents or treatment modalities. To that end, fMRI data will be acquired at baseline and end-of-treatment on all eligible participants to examine (a) resting state connectivity, and (b) response to trauma, substance, and neutral cues. We will continue to work closely with the CAP Co-Is and Neuroimaging Core, directed by [name], to ensure comparability of imaging data acquisition and pre-processing. Scans will be conducted at the MUSC Center for Biomedical Imaging (CBI), which houses a Siemens 3T TIM Trio MRI scanner (Siemens Medical, Erlangen, Germany). The neuroimaging component will involve three visits, each lasting 60-90 minutes and following the same procedures. In visit 1, imagery scripts will be developed according to standardized procedures described by Sinha (Sinha & Li, 2007) and employed in our ongoing research with Veterans. During visits 2 and 3 (see Fig 5), participants will first be screened for metal using a handheld metal detector. Trained staff will position subjects on the scanner bed with foam padding placed around their head to prevent motion. Participants will wear headphones to listen to the audio-recorded scripts. For co-registration and normalization of functional images, a high resolution T1-weighted MPRAGE anatomical image will be acquired with the following parameters: TR = 2100 ms, TE = 4.18 ms, flip angle = 12°, field of view = 256 mm, slice thickness 1.0 mm. The scanning planes will be oriented parallel to the anterior commissure-posterior commissure line. Next, participants will be asked to relax and keep their eyes opened and fixed on a cross-hair for six-minutes while resting state data are collected.

Following the resting state scan, participants will be exposed to trauma, substance and neutral cues. Resting state scans will always occur before trauma and substance cue runs (Fig. 5). We will use a block design

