3. Individuals considered an immediate suicide risk or who are likely to require hospitalization during the course of the study.
4. Previous treatment with doxazosin.
5. Subjects on maintenance anxiolytic, antidepressant, or mood stabilizing medications which have been initiated during the past four weeks. If it is determined, based on clinical criteria, that a subject needs to be started on maintenance medications for anxiety, mood or psychotic symptoms during the course of the study, they may be discontinued from the treatment trial.
6. Women who are pregnant, nursing or not practicing an effective form of birth control.
7. Individuals with a history of or current medical illness including unstable angina, myocardial infarction, congestive heart failure or other cardiac condition, hypotension, renal or hepatic disorders, endocrine disorders, prostate or other cancer, pancreatitis, or a seizure disorder.
8. Subjects with abnormal liver function test (LFTs) as evidenced by laboratory findings of SGOT or SGPT greater than two times normal.
9. Subjects with a history of adverse reactions to quinazolines or other alpha-1-antagonists (such as allergic reactions, priapism, hepatitis, angioedema, or intraoperative floppy iris syndrome).
10. Individuals currently taking alpha blockers (terazosin, prazosin), hypnotics/benzodiazepines, atypical antipsychotics (olanzapine, quetiapine, risperidone, clozapine), alpha-2-agonists (Clonidine, methyldopa, tizanidine, guanfacine), conivaptan, boceprevir, idelalisib, PDE-5 inhibitors or alpha-1-antagonists, protease inhibitors (treatment of HIV), oral antifungals, alfuzosin, pazopanib, silodosin, tadalafil, or tamulosin.
11. MRI exclusions: Claustrophobia; tattoos above the shoulders after evaluation by MRI technician; permanent eyeliner or permanent artificial eyebrows; cardiac pacemaker; metal fragments in eye, skin, or body, including shrapnel; heart valve replacement; brain clips; venous umbrella; being a sheet-metal worker or welder; lifetime history of aneurysm surgery; intracranial bypass, renal, or aortic clips; prosthetic

devices such as middle ear, eye, joint, or penile implants; joint replacements; non-removable hearing aid, neurostimulator, or insulin pump; shunts/stents; metal mesh/coil implants; metal plate/pin/screws/wires; or any other metal implants.

No special classes of subjects, such as, pregnant women, prisoners, institutionalized individuals, or others will be recruited for this study.

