If eligible, participants may be asked to complete two neuroimaging scans (functional magnetic resonance imaging; fMRI), which will be conducted at the MUSC Center for Biomedical Imaging (CBI), which is located at [name] on the MUSC campus (within 2 blocks of the VA). There are very few potential risks from fMRI itself. There is no exposure to ionizing radiation and the machine and scanning sequences and gradients are approved by the Food and Drug Administration (FDA) for routine clinical use. Individuals who are claustrophobic may experience some anxiety during the scanning procedures. A patient may experience some loud noises during the scanning procedure and there is a mild risk of hearing damage if patients are not given hearing protection. All participants in the study will be given hearing protection. Participants may experience psychological discomfort from undergoing the scanning procedure, such as boredom and fatigue. Ferrous objects in the body that are undetected could move during scans. This could lead to tissue damage and hemorrhage. These risks are outlined in the informed consent document. In our past and ongoing studies utilizing fMRI, we have been able to safely complete imaging procedures without undue distress or negative outcomes. This includes research with military Veterans who have current PTSD and co-occurring substance use disorders.

All medications have potential side effects. Side effects that have occurred in clinical trials with doxazosin include dizziness/fainting, fatigue, headache, shortness of breath, diarrhea, abdominal pain, edema, priapism, and hypotension. Doxazosin can cause floppy iris syndrome during cataract surgery. Participants will be informed of all potential side effects associated with doxazosin and closely monitored each week.

Because participants are U.S. military personnel, absolute confidentiality of research records cannot be guaranteed. We will, however, make all possible efforts to protect the privacy and confidentiality of study participants. Participants will be provided with a written informed consent document which specifies the risks and confidentiality protections and limits of study procedures.

Sources of Materials

Data will be in the form of structured clinical interviews conducted by trained Independent Evaluators, self-reported questionnaires, medical record review, urine and breath samples, and neuroimaging data that will be obtained specifically for research purposes.

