All relevant study staff will be required to complete the CBI's MRI safety training class. The course is taught by an American Registry of Radiologic Technologists registered technician. The staff will be trained about safety in the MRI environment, and how to screen oneself and others. The staff will also have knowledge of safety procedures for entering the scanner facility, safely removing participants from the scanner, when and how to quench the magnet and basic emergency procedures including emergency contact information. Standard operating procedures for emergency situations are located on-site. The MRI technician and Drs. [name] and [name] (Co-Is) are authorized to operate the equipment and will be present or available during the scanning sessions. Although there are no known risks of MRI scanning to a developing fetus at 3.0 T, the possibility that risks could be discovered in the future cannot be ignored. Therefore, urine pregnancy tests will be used to exclude pregnant women from study participation. A careful metal screening history will be taken from each participant to assess the possibility of metal devices/implants and will be reviewed by the PI, MRI technician and/or clinical staff who have had extensive training and experience with MRI safety. If the screening yields information that raises a question of safety, the participant will be asked to provide the appropriate documentation (i.e., film) before they are allowed to participate. In addition, participants will be asked to empty their pockets and will be screened with a hand-held ferromagnetic-detector wand. Participants will wear earplugs and/or sound-dampening headphones to decrease the intensity of the scanner noise. Prior exposure to pictures of the scanner, getting into the mock scanner, and seeing others in the scanner, often reduces psychological discomfort or identifies people for whom scanning is not appropriate.

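### The week-12 MRI scan has no pregnancy test scheduled near it: as extracted, Table 1's last test is at week 8, about four weeks earlier

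*Combined protocol and SAP*

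**What the plan says.** Within section 2 (Adequacy of Protection from Risk), the MRI safety paragraph under Protection Against Risk says no fetal risk at 3.0 T is known but that one might yet be found, and concludes: "Therefore, urine pregnancy tests will be used to exclude pregnant women from study participation". It gives no timing relative to either scan.

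The other relevant places are:

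- **Figure 4 caption:** "Neuroimaging scan prior to treatment initiation and again during week 12 prior to medication discontinuation". General Procedures likewise puts the second scan in the final treatment week.
- **Table 1, row "Pregnancy Test for Female Subjects":** as extracted, marks at weeks -1, 4 and 8 and none later.
- **General Procedures:** the baseline medical evaluation includes urine β-"HCG in women with child-bearing potential".
- **Exclusion Criteria, item 6:** "Women who are pregnant, nursing or not practicing an effective form of birth control".
- **Neuroimaging Component:** at each scan visit, "participants will first be screened for metal using a handheld metal detector". Protection Against Risk adds a metal history, a detector wand and hearing protection. Neither place describes a pregnancy test on the day of the scan.

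**The concern.** The plan names an exposure (the scanner) and a safeguard (the urine test), but the schedule does not tie one to the other at the second exposure. The first scan follows a recent baseline test. The second comes four weeks after the last scheduled test, so a pregnancy begun in that interval would not be detected by anything the plan schedules.

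What is at stake is a small precautionary protection for a few women. This is not a contradiction in the plan, and it has no bearing on the trial's inference.

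**Working it through.** **1. Reading the Table 1 row.** The header has 17 cells: a blank, the week label, then weeks -1, 0, 1 to 12, and 18. The pregnancy row also has 17 cells, so it is not cut short. Its marks fall under weeks -1, 4 and 8. The five cells for weeks 9, 10, 11, 12 and 18 are empty.

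**2. Checking the column alignment.**

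| Row | Weeks marked, as extracted | Independent support |
|---|---|---|
| Pregnancy test | -1, 4, 8 | Baseline test confirmed in General Procedures |
| "Clinician Administered PTSD Scale (CAPS-5") | -1, 6, 12, 18 | Sensible pattern: baseline, mid-treatment, end of treatment, follow-up |
| Ethyl glucuronide (EtG) | -1, 0, 4, 8, 12, 18 | EtG entry under Assessment Instruments lists weeks 0, 4, 8, 12 and follow-up |
| Riboflavin | 0, 4, 8, 18 | None; a compliance marker at week 18 but not week 12 is implausible |
| Urine drug screen | -1, 2, 5, 8, 18 | Its text entry says monthly, which this pattern does not match |

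The CAPS-5 and EtG rows support the alignment. The riboflavin and drug-screen rows show that late columns are not fully reliable.

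**3. Age of the result at the second scan.**

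- Nominal: (12 − 8) weeks × 7 = 28 days.
- The plan gives no visit windows. If each visit may fall on any day of its week, week 8 is days 50–56 and week 12 is days 78–84. The interval then runs from 78 − 56 = 22 days to 84 − 50 = 34 days.

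**4. Number of women affected.** The Power section expects about 88 of 144 participants to be scanned. Section 6 (Inclusion of Women and Minorities) puts women at under 8% of the catchment area. The Power section also anticipates about 30% dropout.

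- 0.08 × 88 = 7.0 women.
- With 30% dropout applied to this subset: 7.0 × 0.70 = 4.9.
- Section 6 also predicts a significant minority of women, so 8% is not a firm ceiling. At an assumed 16%: 0.16 × 88 = 14.1, and 14.1 × 0.70 = 9.9.

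Not all of these women would be of child-bearing potential, so these counts err on the high side for a given share of women.

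**5. Expected pregnancies at the second scan.** The documents give no conception rate. I assume 0.1% to 1% over four weeks under the required contraception.

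| Share of women | Low: with dropout, 0.1% | High: no dropout, 1% |
|---|---|---|
| 8% | 4.9 × 0.001 = 0.005 | 7.0 × 0.01 = 0.07 |
| 16% (assumed) | 9.9 × 0.001 = 0.01 | 14.1 × 0.01 = 0.14 |

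**The case against.** The strongest objection is that the point depends on one empty table cell. No prose says that testing stops at week 8, and nearby rows look wrong at the same end of the table. The medication log and riboflavin rows are blank at week 12 but marked at week 18, when participants are off drug. The breathalyzer and Timeline Followback rows show twice-weekly entries at a single follow-up visit. The drug screen does not fit its stated monthly schedule. A four-weekly pregnancy test would naturally continue to week 12, and a broken table is not a fault of the plan.

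This limits confidence but does not dispose of the point. Those rows still carry a late mark, at most in the wrong column. The pregnancy row has no mark after week 8 in any column, so a mark would have had to be lost rather than shifted. No text supplies a later test.

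A second objection is that the MRI safety paragraph commits to pregnancy testing without confining it to the Table 1 dates, so the imaging center may test on the day under its own procedures. That is possible, and unscheduled tests remain open to staff. It is not written in the plan, however, and Table 1 is where staff will look for the schedule.

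Third, the risk is already mitigated by the contraception requirement, weekly staff contact and the absence of a known hazard. All of that stands and is why the point is minor. The contact is only a partial safeguard: some visits may be by telephone and medication may be mailed. If the week-8 test were missed for that reason, the last result would be from week 4, (12 − 4) × 7 = 56 days before the scan.

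**Conclusion.** The concern holds as a minor safety improvement. With Table 1 as extracted, the week-12 scan relies on a pregnancy result nominally 28 days old (22 to 34 days), although scanning is the stated reason for testing. About 5 to 7 women would be affected, or 10 to 14 if women made up 16% of those scanned. The expected number of pregnancies at that scan is a small fraction of one: 0.005 to 0.07, or 0.01 to 0.14 at 16%.

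This rests on three assumptions: that the extracted pregnancy row is complete, that the catchment share of women carries over to the imaging subset, and that the assumed conception range is reasonable. Confidence is medium, mainly because of the first. The change is worth considering because it is cheap, not because harm is likely.

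**What to change.** Make two edits:

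1. In Table 1, add a week-12 urine pregnancy test for women of child-bearing potential having the second scan, done at or shortly before the scan visit.
2. In the Neuroimaging Component section, state that the scan goes ahead only if that test is negative.

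EtG urine is already due in week 12 and can be used if it is collected before the scan. The plan does not say that it is, and the scans are at a separate facility ("which will be conducted at the MUSC Center for Biomedical Imaging (CBI")), so allow for a fresh sample at the imaging visit.

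The cost is one urine test for roughly 5 to 7 women, one table mark and one sentence. The age of the result at the second scan falls from about 28 days to about zero. If the original table already carries a week-12 mark, only the sentence is needed.
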